### *3.11 Blindness*

There will be no blindness at the level of the patient, the treating physicians (surgeon, anesthesiologist) and the researcher who will record the data.

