There are three resection planes: the mesocolic, intramesocolic and muscularis propria plane. The ideal resection plane is the mesocolic, in which the colon is removed, along with the entire mesocolon and all the venous and lymphatic tissue, without violating the visceral fascia [4]. Surgical specimens categorized into either of the other two resection planes are associated with reduced R0 resection rates [6] and with reduced overall survival. Characteristically, the muscularis propria resection plane has been associated with up to 15% reduced survival rate compared to the mesocolic plane [7, 8].

There are specific morphometric characteristics of surgical specimens that are used to assess their quality. These include tumor and proximal colon high vascular ligation distance, number of lymph nodes, length of resected small bowel and colon, and total area of the mesocolon [7, 8]. These characteristics are directly related to the number of harvested lymph nodes and, therefore, to overall survival [7, 8].

According to initial results, CME specimens were larger in size, contained a longer length of colon, a larger mesenteric surface and a greater number of lymph nodes compared to the standard colectomy specimens [3]. In addition, a greater distance of the tumor from the resection margins was highlighted [3]. Specifically for right colon cancers, recent publications [6–8, 11–14] have shown that CME can achieve better morphometric specimen characteristics and a greater number of lymph nodes. In a recent randomized study, Di Buono et al. [15] compared the completion of CME or not, during laparoscopic right colectomy. A significant difference was found in favor of CME, regarding the specimen length and the lymph node harvest.

Despite these, the literature evidence regarding the morphological and qualitative characteristics of laparoscopic and open CME specimens are still inconclusive. Specifically for right colectomies, in the comparative study by Gouvas et al. [6], it was observed that the percentage of the mesocolic resection level was 100% in open colectomy, in contrast to 85.7% in the laparoscopic approach. However, this difference was not statistically significant. In a retrospective study by Ali Koc et al. [17], no difference was found between open and laparoscopic CME in terms of specimen length, R0 resection rate and number of resected lymph nodes. A recent

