publication by Ali Zedan et al. [18], argued that open CME is associated with longer specimens, larger mesenteric area, and increased resection margins. Another interesting finding was that the number of lymph nodes and the distance of the ligation site were greater in the laparoscopic CME group. However, the meta-analysis by Anania et al. [19] failed to validate any difference between the two methods in the total number of lymph nodes. Finally, a comparative analysis of our own series of patients did not show superiority of one technique over the other in terms of resection level, specimen length and number of lymph nodes [20].

Additional qualitative characteristics of a colon cancer operation include operative time, intraoperative blood loss, time of bowel function recovery, length of postoperative hospital stay, postoperative complications, as well as overall survival and local recurrence rate [2, 6, 8–10]. In a recent meta-analysis by Anania et al. [16] applying the principles of CME to right colectomies did not affect the rates of postoperative leaks, bleeding, overall complications, and reoperations. However, CME right colectomy was associated with optimal results in terms of 3-year overall survival and 5-year disease-free survival [16].

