### *3.7 Primary endpoint*

Mesocolic Resection Plane. Occurrence of Mesocolic Resection Plane. If such an episode occurs, then it will be defined as=1 'YES' If such an episode does not occur, then it will be defined as=0 'NO'. [Time Frame: 1 month postoperatively]

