### *3.9 Calculation of the sample size*

Sample size calculation was based on the primary outcome. According to the literature [6] the percentage of mesocolic plane preservation in open and laparoscopic colectomy is 100% and 85.7%, respectively. Therefore, for  $\alpha=5\%$ , power=80%, 10% dropout rate, and 1:1 allocation ratio, the calculated sample in each group is 57 patients. Therefore, the total sample of the study is 114 patients.

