### *3.10 Randomization*

The randomization of the patients will be performed using a dedicated software with a 1:1 allocation ratio. The allocation group will be concealed with opaque envelopes that will be opened upon entrance of the patient in the operation theatre.

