### *3.13 Monitoring*

Following hospital discharge, the patient will be called for reassessment one month after the operation to evaluate any postoperative complications. At the same time, the pathology report of the specimen and the adjuvant treatment will be recorded. In addition, at 5 years postoperatively, overall, disease-free survival and recurrence rates will be recorded.

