### *3.15 Study Group*

All participating members have years of experience in their field and have, therefore, completed the learning curve for the required techniques. Data collection and recording will be carried out by an independent, third party, researcher.

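### The primary endpoint is a judged yes/no on the specimen, but the protocol neither names nor masks the person who grades it

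*Protocol*

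**What the plan says.** - **Endpoint.** Section 3.7 codes the primary endpoint as a binary at one month: "Occurrence of Mesocolic Resection Plane. If such an episode occurs, then it will be defined as=1 'YES" and 0 otherwise. It names no assessor.
- **What is judged.** Section 1.1 describes three resection planes. The mesocolic one is where "the colon is removed, along with the entire mesocolon and all the venous and lymphatic tissue, without violating the visceral fascia".
- **Masking.** Section 3.11 is the only statement: "There will be no blindness at the level of the patient, the treating physicians (surgeon, anesthesiologist) and the researcher who will record the data". Whoever grades the specimen is not on that list.
- **Source of specimen data.** Section 3.13 says that at the one-month visit "the pathology report of the specimen and the adjuvant treatment will be recorded".
- **Independence.** Section 3.15 says: "Data collection and recording will be carried out by an independent, third party, researcher".
- **Concealment.** Section 3.10 uses "opaque envelopes that will be opened upon entrance of the patient in the operation theatre".
- **Planning rates.** Section 3.9 assumes that "the percentage of mesocolic plane preservation in open and laparoscopic colectomy is 100% and 85.7%, respectively" and arrives at 57 patients per group with 10% dropout.

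**The concern.** Deciding whether the visceral fascia was left intact calls for judgement, and knowing how the operation was done can sway a borderline grade. The operating team cannot be masked in a comparison of open with laparoscopic surgery, but the grading step can be. Section 3.11 goes through the roles one by one and leaves out the role that produces the primary outcome.

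Randomisation protects the comparison up to the operation. It does not remove a bias that enters when the specimen is graded, and no analysis plan can restore masking afterwards. Because the endpoint is binary with few expected failures, a handful of grades settles the result.

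**Working it through.** **1. Does any section fill the gap?**

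- 3.7 gives the coding and time frame, and no assessor.
- 3.13 has the pathology report recorded. It does not say that the plane grade comes from that report, or what its author knows of the approach.
- 3.15 makes the recorder independent. Recording is not grading, and 3.11 declares the recorder unblinded.
- 3.10 conceals allocation only until the patient enters theatre, before any specimen exists. Nothing later keeps it from the grader.

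The protocol therefore does not say that the grader is unmasked. It is silent, and nothing in it prevents unmasked grading.

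**2. The plan's own figure.** Inputs from 3.9: 100% and 85.7%, α = 5% (two-sided assumed), power 80%, 10% dropout, 1:1. With the pooled-variance formula without continuity correction and a mean rate of 0.9285:

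n = [1.960·√(2·0.9285·0.0715) + 0.842·√(0.857·0.143)]² / 0.143² = 49.8, so 50 per arm; 50/0.9 = 55.6, so 56.

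The stated 57 is within one patient. The sample size is not in dispute here.

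**3. How many gradings decide the result.** Evaluable per arm: 57 × 0.9 = 51.3, taken as 51. Expected laparoscopic failures: 51 × 0.143 = 7.3. Section 3.9 names no test, so both Fisher's exact test and the uncorrected chi-square are shown.

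| Failures of 51, open vs laparoscopic | Fisher p | Chi-square p |
|---|---|---|
| 0 vs 7 | 0.0125 | 0.0061 |
| 1 vs 7 | 0.060 | 0.027 |
| 1 vs 6 | 0.112 | 0.0502 |
| 2 vs 7 | 0.160 | 0.081 |
| 0 vs 5 | 0.056 | 0.022 |
| 0 vs 4 | 0.118 | 0.041 |
| 0 vs 3 | 0.243 | 0.079 |

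Starting from 0 vs 7, one open specimen downgraded loses significance under Fisher; two regradings lose it under chi-square (1 vs 6, or 2 vs 7). If only laparoscopic failures are upgraded, it takes two under Fisher and four under chi-square.

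**4. Illustrations of differential grading.** The bias rates are assumptions; the documents give none. Rejection probabilities come from summing the two binomial distributions over all tables at 51 per arm, two-sided 5%, and are shown as Fisher / chi-square.

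*Equal true rates, so every rejection is a false positive:*

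| True rate, both arms | No bias | 5% of laparoscopic successes downgraded | Half of open failures upgraded |
|---|---|---|---|
| 85.7% | 2.4% / 4.8% | 5.2% / 8.6% | 11.9% / 20.9% |
| 90% | 1.8% / 4.9% | 5.4% / 10.2% | 6.6% / 14.7% |
| 93% | 1.3% / 4.6% | 5.7% / 12.1% | 3.2% / 10.8% |
| 95% | 0.75% / 4.4% | 6.0% / 13.8% | 1.3% / 7.7% |
| 97% | 0.2% / 2.9% | 6.1% / 16.9% | 0.2% / 3.3% |

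The 93% row is about the midpoint of 100% and 85.7%. Five percent of laparoscopic successes is 2.2 to 2.5 specimens across these rows.

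*True 100% vs 85.7%:*

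- No bias: 76% / 95%.
- 5% of laparoscopic successes downgraded (0.857 × 0.95 = 81.4%): 93% / 99%, so the difference is exaggerated.
- A quarter of laparoscopic failures upgraded (85.7% + 14.3%/4 = 89.3%; 7.3/4 = 1.8 specimens): 47% / 81%, so power is lost.

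**The case against.** The strongest reply is that this is an argument from silence. Section 3.11 lists who is unblinded, and the grader is not on the list. The primary endpoint's one-month time frame matches the visit at which 3.13 records the pathology report, so the grader is evidently a pathologist. That inference about identity is reasonable, but it says nothing about masking: a pathologist can know the approach.

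The second reply is that the fragility depends on the test. The sample size is reproduced by the formula that corresponds to the uncorrected chi-square, and under that test a single regrading changes nothing (1 vs 7, p = 0.027). The two-specimen case of 1 vs 6 only just fails, at 0.0502. This is correct. Moreover, any binary endpoint of this size is about as fragile, so the p-values show how few gradings matter and not that grading is biased.

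The third reply is that the bias rates are invented. They are assumed, and some give little: the Fisher figures of 5.2% to 6.1% are barely above the nominal 5%, and upgrading half of open failures has almost no effect at a true 97%. Nor is a direction documented. The planning study has open surgery ahead, while the team's own series "did not show superiority of one technique over the other in terms of resection level". These limits bear on the size of the effect. They leave the gap in place.

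**Conclusion.** The point holds. The protocol allows a judged primary endpoint to be graded with the approach known, and it does not name the grader. That is more than a missing detail, because masking has to be in place before the first specimen is graded.

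The direction and size of any bias are unknown. If about two specimens per trial were graded differently because of the approach, false positives could reach 5.2–6.1% (Fisher) or 8.6–16.9% (chi-square) over common true rates of 85.7% to 97%. In the other direction, power at the planned difference could fall from 76% to 47% or from 95% to 81%. These figures rest on 51 evaluable patients per arm, a two-sided 5% level and assumed bias rates. This is a change that should be made. Confidence is medium, because the actual grading practice is not described.

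**What to change.** In 3.7, name the role that grades the plane. This is presumably the pathologist who already reports the specimen, but the protocol should say so. In 3.11, add wording such as:

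> The resection plane is graded masked to allocation, from a specimen and request form carrying the study number and tumour site but not the surgical approach. The grade is recorded before allocation is disclosed and is transcribed unchanged.

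If masking proves unworkable, 3.11 should at least say that the grader is unmasked. That discloses the weakness without removing it.

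The cost is two or three sentences, a coded request form and a sign-off step. If the reporting pathologist grades, no extra reader is needed, and sample size and patient care are unaffected. There are two downsides: the documents do not show whether the pathology service can work from a form that omits the approach, and masking may be incomplete if the specimen itself hints at it.

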### *3.12 Exit criteria*

The patient will be discharged when it is ensured that is medically safe to be released. The exit time will be regarded as the time that the patient will fulfill the Clinical Discharge Criteria. More specifically, the patient should display the following: steady vital signs, fully oriented, without nausea or vomiting, mobilized with a steady gait and without a notable bleeding [22].

### *3.13 Monitoring*

Following hospital discharge, the patient will be called for reassessment one month after the operation to evaluate any postoperative complications. At the same time, the pathology report of the specimen and the adjuvant treatment will be recorded. In addition, at 5 years postoperatively, overall, disease-free survival and recurrence rates will be recorded.

### *3.14 Medication*

Both preoperative and postoperative patient treatment will be standardized. The principles of the ERAS protocols will be applied to patients [23]. More specifically, antimicrobial prophylaxis will include the administration of intravenous antibiotics within 60 minutes prior to the onset of operation. Patients will receive preoperative, mechanical bowel preparation and per-os antimicrobial prophylaxis. Prior to surgery, patients will abstain from solid and liquid foods for 6 and 2 hours, respectively. The nasogastric tube will be removed postoperatively and repositioned only in case of ileus. Postoperative analgesia will include a multidisciplinary approach using analgesics (paracetamol, lornoxicam) in combination with dorsal or epidural analgesia. Opioid administration will be avoided. Postoperative nausea and vomiting prophylaxis will include granisetron 3mg / 3ml IV. Mechanical and pharmaceutical thromboprophylaxis will be used. A zero-balance approach to fluid losses will be applied. Mobilization will be initiated from the first postoperative day. Feeding will be initiated on the basis of the intestinal function recovery.

### *3.15 Study Group*

All participating members have years of experience in their field and have, therefore, completed the learning curve for the required techniques. Data collection and recording will be carried out by an independent, third party, researcher.

### *3.16 Conducting a Study*

The study will be conducted in the Department of Surgery of University Hospital of Larissa. Patient data will be recorded both in the patient charts and in an electronic database. The required laboratory examinations will be defrayed by the patient insurance funds.

